2.2 Secondary objectives

- 2.2.1** To determine disease control rate (DCR), defined as the percent of patients (relative to the total number evaluable) who achieve CR, PR, or stable disease (SD) at the time of ORR assessment.
- 2.2.2** To estimate DOR, defined as the time from achievement of PR or CR to progression of disease (POD) according to Lugano criteria.^{1,2}
- 2.2.3** To estimate PFS, defined as the time from initiation of study treatment to the earlier of POD or death from any cause.
- 2.2.4** To estimate OS, defined as the time from initiation of study treatment to death from any cause.
- 2.2.5** To estimate TTP, defined as the time from initiation of study treatment to POD or death from MCL.
- 2.2.6** To describe the safety of the combination of tafasitamab and lenalidomide in patients with R/R MCL, defined as the incidence and severity (according to National Cancer Institute Common Terminology Criteria for Adverse Events (CTCAE) version 5.0).

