10.4 Study duration

The maximum duration of treatment for this study is planned to be a total of 36 cycles (12 cycles of tafasitamab plus lenalidomide induction, 24 cycles of tafasitamab maintenance), not to exceed 36 months.

After discontinuation of both study drugs, patients will complete an EOT visit within 7 days from the date of official treatment discontinuation. If treatment must be discontinued due to prolonged interruption for toxicity (see 10.5.7), the EOT visit will occur within 7 days of the decision to permanently discontinue treatment.

All patients will be followed for adverse events for at least 30 days following the last dose of study treatment or until initiation of new therapy, whichever comes first. Patients who proceed to tafasitamab maintenance will be followed for disease status updates for up to three years. After completing study treatment, survival, relapse, and new anti-lymphoma therapy information will be collected via telephone calls, patient medical records, and/or clinic visits approximately every 6 months until death, loss to follow up or consent withdrawal, whichever comes first.

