12.0 CRITERIA FOR REMOVAL FROM STUDY

Patients may voluntarily withdraw from the study or be removed from the study at the discretion of the investigator at any time. Patients may be withdrawn from the study if any of the following occur:

- Disease progression
- Ineligibility (at the cycle 1 day 1 evaluation or earlier) as defined in the inclusion/exclusion criteria
- Treatment will be discontinued at the request of the patient, refusal of therapy, non-compliance, or upon development of an intercurrent significant medical illness
- Significant protocol violation
- Unacceptable toxicity necessitating drug discontinuation as outlined in 10.5
- Decision by the investigator that termination is in the patient's best medical interest
- Loss to follow-up
- Development of active HBV, HCV, or HIV infection
- Pregnancy or positive pregnancy test
- Death of the patient
- Start of any other antineoplastic therapy

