13.2 Criteria for Study Endpoint Evaluability

All patients who received at least one dose of tafasitamab and one dose of lenalidomide will be considered evaluable for the primary endpoint of ORR and all secondary endpoints. This will be the primary analysis. Safety endpoints will be evaluated in all patients who received at least one dose of tafasitamab or one dose of lenalidomide. Any patient that is removed from the study for reasons other than progression will be counted as a failure for ORR analysis and as an event for PFS analysis (as long as they have received at least 1 dose of tafasitamab and 1 dose of lenalidomide). For OS analysis, patients who are removed from the study for any reason other than death will be censored at the time of study removal. The study will continue enrollment until the required number of evaluable patients (those that receive at least one dose of both study drugs) is reached in each stage of the study.

The primary and secondary endpoints will also be evaluated in the per-protocol cohort (patients who did not have any major protocol violations) as a supportive, secondary analysis.

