15.2 External SAE Reporting

SAE Reporting to Incyte

The Principal Investigator (PI) must report all SAEs to Incyte within 24 hours of learning of an event, regardless of the PI's causality assessment. This notification should be provided on a completed SAE form. SAE reporting for each subject begins the day the informed consent is signed by the patient and within 30 days after subject has completed or discontinued from the study or has taken last dose of the study drug, or as described in the protocol.

SAEs, occurring using Incyte study drug, are reported in accordance with the effective protocol. SAEs occurring with any other commercial drug are reported to the manufacturer of that drug in accordance with regulations and protocol.

Initial SAEs and/or subsequent follow-up reports should be reported via email to [contact] or fax(+) [name]. SAE reports should be for a single subject. SAE forms should be sent with a cover sheet and any additional attachments.

All SAEs incurred while a patient is on study will be reported to the IRB at MSKCC and Incyte. All SAEs and relevant laboratory findings will be reported to the principal investigator immediately. All information regarding SAEs must be recorded on the form provided. Patient suffering SAEs must be carefully followed and all follow-up information also recorded.

All life-threatening and lethal known, unknown, or suspected reactions must be reported to the principal investigator. It is the treating physician's responsibility to investigate and report the date and cause of death of any patient entered on this trial.

Reporting of Pregnancy to Incyte

An "Initial Pregnancy Report" or equivalent must be completed in full and emailed to [contact] or faxed to (+) [name] within 24 hours of discovery of a pregnancy of a subject who has taken the Incyte product. The "Follow-up Pregnancy Report Form" or equivalent must be completed and emailed to [contact] or faxed to (+) [name] within 30 days after delivery, so that Incyte is provided with information regarding the outcome of the pregnancy. If the pregnancy results in any events which meet the serious criteria (i.e., miscarriage or termination), the SAE reporting process needs to be followed and the timelines associated with a SAE should be followed.

The SAE report should be completed as per above instructions. If appropriate, the report will be forwarded to the FDA by the IND Office.

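### Read as written, the OS censoring rule in 13.2 leaves out known deaths after removal for progression, toxicity or new therapy, and it conflicts with the survival follow-up in 10.4

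*Combined protocol and SAP*

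**What the plan says.** Section 2.2.4 states the objective: "To estimate OS, defined as the time from initiation of study treatment to death from any cause". Section 14.0 repeats this definition, plans a Kaplan-Meier estimate with a 95% confidence interval, and uses OS in exploratory Cox models of genomic alterations. It gives no censoring rule for OS.

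The only such rule is in Section 13.2: "patients who are removed from the study for any reason other than death will be censored at the time of study removal". The sentence before it in 13.2 begins: "Any patient that is removed from the study for reasons other than progression will be counted as a failure for ORR analysis".

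Section 12 opens its list of removal reasons with "Patients may be withdrawn from the study if any of the following occur". The list includes disease progression, unacceptable toxicity, loss to follow-up, death, and "Start of any other antineoplastic therapy".

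Section 10.4 describes follow-up: "After completing study treatment, survival, relapse, and new anti-lymphoma therapy information will be collected via telephone calls", among other sources, "approximately every 6 months until death, loss to follow up or consent withdrawal, whichever comes first". Section 15.2 makes it the treating physician's "responsibility to investigate and report the date and cause of death of any patient entered on this trial".

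**The concern.** The 13.2 rule exempts death and nothing else. A patient removed at progression, for toxicity or at the start of another therapy would be censored for OS on that date, and a later death would not count even when its date is known.

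Kaplan-Meier and Cox methods assume that a censored patient has the same outlook as a similar patient still under observation. A patient removed for one of these reasons generally does not. The OS curve and the exploratory Cox models on OS would then depend on who was removed and when, which Section 12 leaves to discretion. The confidence interval would not show this.

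Censoring at genuine loss to follow-up, also on the Section 12 list, is standard and not at issue.

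**Working it through.** **1. Does removal include progression?** The sentence before the OS rule sets apart removals for reasons other than progression, which makes sense only if progression is a kind of removal. Section 12 lists both progression and death as removal reasons, so a rule that exempts only death leaves progression in.

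**2. Which sections conflict?**

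| Section | Content | Bearing on 13.2 |
|---|---|---|
| 2.2.4, 14.0 | OS event is death from any cause | Defines the event. A censoring rule is needed alongside it, so the problem is the rule's scope |
| 10.4 | Survival, relapse and new therapy collected until death, loss to follow-up or consent withdrawal | Firm conflict: progression and new therapy do not end this follow-up, but 13.2 stops counting there |
| 15.2 | Date and cause of death for any patient entered | Supporting only, since it sits in the section on SAE reporting |

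**3. The plan's own figures.** The plan states no OS sample size, event count or precision target. Its only design figures are for response rate. The exact two-stage calculation (sum over 7 to 19 stage 1 responders of their probability times the chance of reaching 17 of 39) gives 80.4% power at 50% and a type I error of 4.55% at 30%. This agrees with the stated 80% and 5%, and OS does not enter it.

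**4. Illustration of size.** All inputs are assumptions:
- median PFS 6 months, so a = ln 2/6 = 0.1155 per month;
- post-progression median 5.8 months, so m = ln 2/5.8 = 0.1195. Section 3.0 gives 5.8 months as median OS after BTKi failure; it is only a stand-in here;
- share of first events that are deaths, d = 0.2;
- r, the share of progressors removed at progression.

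Alive without progression: S(t) = exp(-at). Alive after progression: P(t) = (1-d)·a·[exp(-at) - exp(-mt)]/(m-a). True OS is S + P. At 12 months, S = 0.250 and P = 0.271, so true OS is 0.521, or 52%.

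With a share r censored at progression, Kaplan-Meier estimates the curve with hazard [d·a·S + m(1-r)P]/[S + (1-r)P]. I integrated this numerically:

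| r | 12-month OS under 13.2 | Overstatement (points) |
|---|---|---|
| 25% | 55.5% | 3.4 |
| 50% | 60.0% | 7.9 |
| 75% | 66.3% | 14.2 |
| 100% | 75.8% | 23.7 |

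The last row can be checked by hand. At r = 1 the hazard is d·a = 0.0231, and exp(-0.0231 × 12) = 0.758.

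**5. Deaths left out.** With 39 patients each followed 24 months, S(24) = 0.0625 and P(24) = 0.132, so deaths number 39 × (1 - 0.1947) = 31.4. Deaths without progression are 39 × 0.2 × (1 - 0.0625) = 7.3, leaving 24.1 after progression. At r = 25%, 6.0 are left out; at r = 50%, 12.1.

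**6. Direction.** Removal shifts weight from hazard m to hazard d·a. The bias is upward when m > d·a, that is, when the post-progression median is shorter than median PFS divided by d (here 6/0.2 = 30 months). Over 36 combinations (PFS 2, 3, 4, 6, 9 or 12 months; d 10%, 20% or 30%; post-progression median 5.8 or 12 months) it reverses in 3, all with a post-progression median of 12: PFS 2 with d 20% or 30%, and PFS 3 with d 30%. The range is -1.0 to +4.2 points at r = 25% and -2.4 to +10.0 at r = 50%.

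**7. Sampling error.** The 95% half-width for 12-month OS is 1.96·√[s(1-s)/39]: 15.0, 15.7 and 14.4 points at s = 0.35, 0.52 and 0.70, with no other censoring. Over the grid, the shift at r up to 50% is smaller than this.

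**The case against.** The strongest reply is that study removal may mean only leaving the survival follow-up. Section 10.4 has its own terms for stopping drug and goes on to collect relapse and new therapy, which would be pointless if those events ended follow-up. Section 12 is permissive, and one of its items speaks of discontinuing treatment, so it mixes off-treatment with off-study. On that reading, 13.2 is ordinary censoring.

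This stands as a real ambiguity. It does not remove the point: no section states the narrow meaning, and it would give removal from the study two meanings in adjacent sentences of 13.2.

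It is also fair to say that the size rests wholly on assumed inputs, that OS has no threshold or test, and that the illustrated shift at up to 50% removal is within sampling error. These limit the severity. But sampling error is shown by the interval and this bias is not, and the bias can be avoided where deaths are known.

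A reader might go further and infer that the trial's OS will be grossly overstated. In the illustration the median would move from 12.6 to 6/0.2 = 30 months if every progressor were removed. The documents do not support that as a forecast, because Section 12 only permits removal and gives no removal rate. Nor do they support a bias that is always upward (step 6), or any effect on the response-rate conclusion.

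**Conclusion.** The point holds as a defect of the text: the only OS censoring rule, read as written, excludes deaths that 10.4 collects, and it censors for reasons related to prognosis. It should be fixed. Confidence is high on the wording and the conflict with 10.4, and much lower on the size.

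The actual effect ranges from almost none, if removal means leaving survival follow-up, to double-digit shifts in 12-month OS, if most progressors are removed at progression. The illustration assumes constant hazards and covers removal at progression only. Bias from removal for toxicity or new therapy, and the effect on the Cox models, were not quantified. The 6 of 19 and 17 of 39 response rules are unaffected.

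**What to change.** Replace the OS sentence in 13.2 with:

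> *For OS, every known death in evaluable patients is an event, regardless of progression, treatment discontinuation, removal under Section 12 or new therapy. Patients not known to have died are censored at the date last known alive (data cutoff, loss to follow-up or withdrawal of consent for follow-up).*

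State in 10.4 that survival follow-up applies to all treated patients, including those who stop early. State in Section 12 that, for OS, stopping treatment or removal under that section does not end survival follow-up unless the patient is lost or withdraws consent for it. Leave the response-rate and PFS rules in 13.2 out of this change. Censoring at removal may be kept as a labelled sensitivity analysis.

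The cost is one replaced sentence and two clarifications. If 10.4 now covers only patients who complete treatment, six-monthly survival contacts for early stoppers are added work. If it already covers everyone, there is none. Section 15.2 may supply some death dates but should not be relied on as the source for long-term follow-up.

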14.0 BIOSTATISTICS

Objectives:

The primary objective is to estimate the ORR, defined as the percent of patients (relative to the total number considered evaluable as in 13.2) who achieve CR or PR. The primary endpoint will be analysed when all patients have completed 12 cycles of treatment or at treatment discontinuation, whichever comes first.

Secondary objectives are estimates of OCR, DOR, PFS, OS, and TTP, and descriptions of incidence and severity of AEs. Exploratory objectives include rate of conversion to undetectable MRD, ctDNA/clonal evolution, antitumor immune response, and effects on tumor microenvironment immunosuppression.

Exploratory objectives are described in Section 3.1 Correlative studies.

Study design:

The primary endpoint is ORR and the study is designed to determine preliminary clinical effectiveness of tafasitamab and lenalidomide. Based upon limited data available for lenalidomide and associated combinations in the post-BTKi setting, the combination of tafasitamab and lenalidomide will be considered worthy of further evaluation if the ORR is greater than 30%. This combination will be considered promising in the R/R setting if the ORR is greater than 50% given multiple evolving treatment options for patients post-BTKi failure or intolerance. To this end, , a single-arm Simon's two-stage minimax design will

utilize a null (non-promising) ORR of 30% and an alternative (promising) ORR of 50%. In the first stage, a total of 19 patients will accrue. If 6 or fewer have objective response, the trial will close due to a lack of efficacy; otherwise, an additional 20 patients will accrue. If at the end of the study, 17 or more out of 39 have an objective response, the trial will be considered promising for future development. This design will give 80% power with a type I error rate of 5%. Patients will continue to enroll without holding enrollment while the interim analysis is evaluated in the first 19 patients.

The anticipated accrual rate for this study is 1 to 2 patients per month. We anticipate total accrual will be completed in 2-3 years. The study will continue enrollment until the required number of evaluable patients (those that receive at least one dose of both study drugs) is reached in each stage of the study.

Methods:

Primary objectives: ORR will be calculated as a proportion and summarized along with 95% confidence intervals. Patients who withdraw prior to response evaluation will be classified as nonresponders for the primary objective.

Secondary objectives: OCR will be defined as the percent of patients who achieve CR, PR or stable disease (SD) at the time of ORR assessment. Patients who withdraw prior to response evaluation will be classified as failures. The OCR will be estimated by proportion along with 95% confidence intervals. DOR will be defined as the time from achievement of PR or CR to progression of disease (POD) according to Lugano criteria or death. PFS will be defined as the time from initiation of study treatment to the earlier of POD or death from any cause. OS will be defined as the time from initiation of treatment to death from any cause. Kaplan-Meier estimates of DOR, PFS, and OS will be calculated and presented with 95% confidence intervals. TTP will be defined as the time from start of treatment to POD or death specially from MCL, and will be estimated with 95% confidence intervals by cumulative incidence function. Death from other causes will be treated as a competing risk. Frequency and severity of adverse events will be summarized descriptively.

Exploratory objectives will be performed in conjunction with collaborating laboratories at MSK. Study designs and analytic approaches are detailed in Section 3.1. Most objectives will be summarized descriptively. For assessing association between minimal MRD and PFS, the log rank test will be used and Kaplan-Meier curves will be presented. For assessing association between genomic alterations discovered through MSK-IMPACT sequencing and time-to-event outcomes PFS and OS, Cox regression will be used and hazard ratios with 95% confidence intervals will be presented. For assessing association between genomic alterations and ORR, Fisher's exact test will be used, and p-values will be adjusted for multiple testing with the false discovery rate (FDR).

14.1 Populations for analysis include the following:

- Primary analysis (primary endpoint and all secondary endpoints): All patients who received at least one dose of tafasitamab and one dose of lenalidomide
- Safety analysis: All patients who received at least one dose of tafasitamab or one dose of lenalidomide
- Secondary per-protocol analysis (primary endpoint and all secondary endpoints): All patients who did not have any major protocol violations, identified for each patient with a protocol violation before database closure

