1.0 PROTOCOL SUMMARY AND/OR SCHEMA

This is a single-center, open-label phase II study of the combination of tafasitamab and lenalidomide in relapsed or refractory (R/R) mantle cell lymphoma (MCL) who have received previous treatment with a Bruton's tyrosine kinase inhibitor (BTKi). The study aims to evaluate the efficacy of the combination therapy. The primary endpoint will be objective response rate (ORR) to tafasitamab and lenalidomide, and will be evaluated when all patients have completed 12 cycles of treatment or at treatment discontinuation, whichever comes first.

Patients will be enrolled to receive tafasitamab via IV infusion and self-administer lenalidomide orally according to the treatment schema below, for a maximum of 36 cycles (3 years). In the first stage of the Simon 2-stage design, a total of 19 patients will accrue. If 6 or fewer have objective response, the trial will close due to a lack of efficacy; otherwise, an additional 20 patients will accrue. If at the end of the study, 17 or more out of 39 have an objective response, the trial will be considered promising for future development.

[figure not shown]
The anticipated accrual rate for this study is 1 to 2 patients per month, and the trial will continue through three years after the last accrued patient.

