2.0 OBJECTIVES AND SCIENTIFIC AIMS

2.1 Primary objective

The primary objective of this study is to assess the ORR, defined as the percent of patients (relative to the total number considered evaluable as in 13.2) who achieve complete response (CR) or partial response (PR) according to the 2014 Lugano response criteria for non-Hodgkin lymphoma (NHL), to the combination of tafasitamab and lenalidomide in patients with R/R MCL who have experienced failure of or intolerance to past treatment with BTKi.^{1,2}

Figure 1: Treatment schema

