4.0 OVERVIEW OF STUDY DESIGN/INTERVENTION

4.1 Design

A single-center, single-arm, open-label phase II study evaluating the combination of tafasitamab and lenalidomide for treatment of adults with R/R MCL who have previously failed or could not tolerate BTKi therapy. Patients will be eligible if they have received one or more prior lines of therapy, one of which must have been a BTKi. Patients will be enrolled according to a Simon two-stage design, described in 14.0, with early stop criteria for lack of efficacy.

Tafasitamab will be administered intravenously and lenalidomide will be self-administered orally according to the treatment schema in 4.2. The primary endpoint is ORR (CR plus PR)

[figure not shown]

evaluated by PET/CT according to Lugano criteria at the end of cycle 12 or treatment discontinuation, whichever is earlier.^{1,2}

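### The 6-of-19 futility count has no reading time while enrolment stays open; closing enrolment at the 13th final non-responder among the first 19 makes the same stop earlier at little cost

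*Combined protocol and SAP*

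**What the plan says.** The stage 1 rule in Section 14.0 reads "If 6 or fewer have objective response, the trial will close due to a lack of efficacy". Neither that section nor Section 1.0 says at which assessment those responses are counted. Accrual is deliberately left open: "Patients will continue to enroll without holding enrollment while the interim analysis is evaluated in the first 19 patients".

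A time point exists for the primary endpoint. Section 4.1 places the PET/CT evaluation "at the end of cycle 12 or treatment discontinuation, whichever is earlier", and Section 14.0 times the analysis the same way: "The primary endpoint will be analysed when all patients have completed 12 cycles of treatment or at treatment discontinuation, whichever comes first". Section 2.1 counts patients "who achieve complete response (CR) or partial response (PR) according to the 2014 Lugano response criteria".

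On pace, Section 1.0 says "The anticipated accrual rate for this study is 1 to 2 patients per month" and Section 14.0 says "We anticipate total accrual will be completed in 2-3 years".

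On who fails, Section 13.2 says "Any patient that is removed from the study for reasons other than progression will be counted as a failure for ORR analysis", provided the patient had at least one dose of each drug. The Methods part of Section 14.0 classes patients who withdraw before response evaluation as non-responders.

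**The concern.** A futility stop protects patients only if it comes before most of stage 2 has been enrolled. With a reading that can take up to 12 cycles and no pause in accrual, much of stage 2 may already be on study when the 19th outcome is known. The plan does not ask anyone to act when the result is settled earlier, although the 13th final non-response among the first 19 settles it.

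A running tally works only if everyone agrees who is a non-responder. As worded, Section 13.2 would fail a patient with a documented CR or PR who is then removed for a reason such as toxicity. That would make a stop more likely for an active regimen.

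**Working it through.** **1. The plan's own figures.** Inputs from Section 14.0: null ORR 0.30, alternative 0.50, stop at 6 or fewer of 19, success at 17 or more of 39.

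P(stop) = P(X ≤ 6), with X ~ Bin(19, p). P(success) = Σ (x = 7 to 19) P(X = x) · P(Bin(20, p) ≥ 17 − x).

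- p = 0.30: P(stop) = 0.6655; type I error = 0.0455; expected N = 19 + 0.3345 × 20 = 25.7.
- p = 0.50: P(stop) = 0.0835; power = 0.8036.

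The stated 80% and 5% are reproduced.

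**2. Enrolment if patient 19 stays to cycle 12.** The lag is 12 × 28 = 336 days, and 336 / 30.4375 = 11.04 months. Enrolled = 19 + rate × 11.04, in whole patients. Expected N = 0.6655 × enrolled + 0.3345 × 39.

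| 39 patients in | Rate per month | Enrolled | Stage 2 patients spared by a stop | Expected N at 30% |
|---|---|---|---|---|
| 36 months | 1.083 | 30 (30.96) | 9 | 33.0 |
| 30 months | 1.300 | 33 (33.35) | 6 | 35.0 |
| 24 months | 1.625 | 36 (36.94) | 3 | 37.0 |

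If stage 1 were read at cycle 3 instead (84 days = 2.76 months, assumed), 21 to 23 would be enrolled and expected N would be about 27 to 28. The unstated time point therefore matters.

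**3. Allowing for early discontinuation.** Step 2 is the late-reading case, since a patient who stops earlier is read earlier. The figures below are mean enrolment in trials that stop, at 30% ORR, from simulation with Poisson accrual.

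Assumptions: a fraction of non-responders holds stable disease (SD) to cycle 12. The rest leave at exponential times with median 8.4 weeks (the treatment duration of the whole retrospective post-BTKi lenalidomide cohort in Section 3.0, used as a proxy) or 26 weeks (assumed). Responders stay to cycle 12, except in the last column, where they leave after cycle 3 with a median of 20 weeks (that cohort's median DOR; assumed form). Each cell gives 1.08 / 1.30 / 1.63 patients per month.

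| SD fraction | Median, others | Waiting for all 19 | At 13th final non-responder | Saving | Saving, responders also leave |
|---|---|---|---|---|---|
| 0 | 8.4 wk | 28.7 / 30.9 / 34.0 | 20.7 / 21.7 / 23.1 | 8.0 / 9.2 / 10.9 | 6.1 / 7.1 / 8.4 |
| 0 | 26 wk | 29.9 / 32.2 / 35.3 | 25.4 / 27.4 / 30.4 | 4.5 / 4.8 / 4.9 | 3.8 / 4.1 / 4.1 |
| 0.5 | 8.4 wk | 30.4 / 32.6 / 35.6 | 26.6 / 28.7 / 32.0 | 3.8 / 3.9 / 3.6 | 3.3 / 3.4 / 3.2 |
| 0.5 | 26 wk | 30.6 / 32.8 / 35.8 | 27.6 / 29.9 / 33.1 | 3.0 / 2.9 / 2.7 | 2.6 / 2.6 / 2.3 |
| 1 | – | 30.9 / 33.2 / 36.1 | 28.9 / 31.2 / 34.4 | 2.0 / 2.0 / 1.7 | 1.8 / 1.8 / 1.5 |

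At 2 per month the saving runs from about 1 (all in SD) to about 12 (none in SD, 8.4 weeks).

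**4. Operating characteristics.** Among 19 patients, 13 or more non-responders is the same event as 6 or fewer responders (19 − 13 = 6). With one definition throughout, P(stop), type I error and power stay as in step 1.

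**5. Effect of the Section 13.2 wording.** If a share q of responders (assumed) is removed for reasons other than progression and counted as failures, the counted rate at a true 50% is 0.5 × (1 − q).

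| q | Counted rate | P(stop at stage 1) | Power, if the same rule governs 17/39 |
|---|---|---|---|
| 0 | 0.500 | 8.4% | 80% |
| 5% | 0.475 | 12.3% | 71% |
| 10% | 0.450 | 17.3% | 60% |
| 20% | 0.400 | 30.8% | 36% |

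**6. Two ways to misapply the tally.** If the 13 were counted over everyone enrolled (8.4-week assumption), power would fall to about 16–36%. If SD on treatment were counted as final at an early scan and 10%, 20% or 30% of responders responded later (assumed), power would fall to 74%, 64% or 49%.

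**The case against.** The sponsor declared open enrolment and chose a minimax design, so expected sample size was not its main criterion. Nothing in Section 14.0 forbids acting once the stop is certain, and Section 16.4 has a monitoring committee reviewing from the first enrolment. The benefit also rests on inputs the documents lack. Section 4.2 plans maintenance for patients in SD at cycle 12, so durable SD is expected to occur, and the 8.4 weeks covers responders and mixed lenalidomide regimens. All of this stands. It limits the point to an optional improvement, although general oversight in Section 16.4 is no substitute for a stated trigger.

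A reader might go further in four ways that the documents do not support:

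- *The stage 1 stop is empty because all 39 will be enrolled.* That needs at least 20 / 11.04 = 1.81 per month with patient 19 staying to cycle 12. This is inside the stated 1 to 2 per month but completes accrual in 21.5 months, faster than the stated 2 to 3 years.
- *Type I error or power is damaged by open enrolment.* Neither is.
- *Sections 13.2 and 14.0 contradict each other.* Section 14.0 does not say that only early withdrawals fail, so it is compatible with the broader rule. The difficulty is the breadth of Section 13.2.
- *The remedy is to tie stage 1 to a reading at cycle 12 only.* If an earlier reading was intended, that would create the overrun. Read literally, it could also turn a patient who responded and then progressed into a non-responder.

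**Conclusion.** This is a cheap improvement to a valid design. If the stage 1 count waits for all 19 readings at cycle 12 or discontinuation, mean enrolment in stopped trials is about 29 to 36 at the 2 to 3 year pace (30 to 36 if patient 19 stays to cycle 12). With responders also leaving early it can be as low as about 27 (20.7 + 6.1). That the count waits in this way is an inference, since the rule states no time point.

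Acting at the 13th final non-responder saves about 4 to 11 patients in stopped trials with no durable SD, 2 to 4 with half and 1 to 2 with all. The saving is positive in every scenario run, but its size cannot be fixed from the documents. The definition issue does not depend on the trigger; its size depends on the assumed removal rate.

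**What to change.** In Section 14.0 keep 6/19, 17/39 and open enrolment, and add:

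> Enrolment closes for futility as soon as 13 of the first 19 evaluable patients are final non-responders, because 7 responses are then impossible.

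State with it:

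- Only the first 19 evaluable patients count towards the 13.
- A final non-responder has left treatment, or reached the end of cycle 12, with no documented CR or PR. A patient in SD who is still on treatment is not yet final.
- A patient with CR or PR documented by the earlier of the end of cycle 12 or discontinuation is a responder, which follows the verb *achieve* in Sections 2.1 and 14.0. The same definition serves the tally, the 6/19 count and the 17/39 count.
- The rule governs enrolment only.

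Amend Section 13.2 to match, so that removal for reasons other than progression counts as an ORR failure only when no CR or PR was documented beforehand. Do not tie the stage 1 count to a cycle 12-only reading.

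The cost is a few sentences, the Section 13.2 amendment before the tally starts, and a running tally of 19 patients. There is no accrual pause, extra scan or change in sample size, and the design's type I error and power stay at 0.0455 and 0.804. The downside is that the gain may be only one or two patients.
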